9.5.1 Efficacy Evaluation

Clinical efficacy will be measured by objective tumor response per RECIST 1.1 criteria. The clinical response is defined as a CR or PR or SD. A 95% confidence interval of response rate will be estimated based on a binomial distribution.

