PF-04518600 was administered intravenously at increasing doses (0.01 – 3 mg/kg) every 2 weeks until disease progression or unacceptable toxicity. Additional biomarker cohorts (opened at each dose level except 0.01 mg/kg) enrolled patients who consented to baseline and on-treatment tumor biopsies for immune profiling by

immunohistochemistry and RNA sequencing. As of 09 March 2016, 31 patients have enrolled in the dose-escalation phase of PF-04518600 study: 0.01 mg/kg (2 patients), 0.1 mg/kg (10 patients), 0.3 mg/kg (8 patients), 1.5 mg/kg (7 patients) and 3 mg/kg (4 patients). There were 25.8% of patients that had previously received ≥ 4 prior therapies for advanced disease. There were no dose limiting toxicities, and no drug-related or immune related grade 3-5 adverse events (AEs) were observed. Drug-related AEs (DRAEs) were all grade 1/2 events and occurred in 21 patients (67.7%). The most common DRAEs were fatigue (29.0%) and decreased appetite (9.7%). Out of 25 patients evaluable for response, 1 patient experienced partial response (PR, - 50%, confirmed), and 15 patients experienced stable disease (SD). Eleven patients remain on treatment, and 5 patients continued treatment for >13 weeks. Assessments of peripheral blood lymphocyte indicated full OX40 receptor occupancy at ≥ 0.3 mg/kg, and maximal memory T cell proliferation at 0.1 and 0.3 mg/kg. These preliminary results demonstrate that PF-8600 is safe up to 3 mg/kg (27).

PF-04518600 will also be studied in combination with utomilumab (PF-05082566 anti-4-1BB mAb) in Protocol B0601002 Part B in patients with advanced or metastatic melanoma, HNSCC, non-small cell lung cancer (NSCLC), bladder, gastric or cervical cancers, who are unresponsive to existing therapies, for whom no standard treatment is available, or who have declined standard therapy (26).

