2.0 STUDY OBJECTIVES AND ENDPOINTS

2.1 Objectives

2.1.1 Primary Objectives

- For Arm D, to establish the safety, tolerability, and dose-limiting toxicities (DLTs) of different treatment combinations of avelumab when administered in combination with a checkpoint agonist with radiation in patients with metastatic solid tumors in order to estimate the maximum tolerated dose (MTD) and select the recommended phase 2 dose (RP2D).
- To correlate pre- and post-treatment CD8 expression with clinical benefit (complete response [CR], partial response [PR], or stable disease [SD] for > 6 months).

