2.2.2 Secondary and Exploratory Endpoints

- Objective response rate determined by radiographic disease assessments per RECIST v1.1 and irRECIST.
- Progression-free survival, defined as the time from Cycle 1 start date until the earliest date of disease progression, as determined by investigator assessment of objective radiographic disease assessments per RECIST v1.1 and irRECIST, or death due to any cause, if occurring sooner than progression.
- Duration of response determined by radiographic disease assessment, defined as the time from earliest date of disease response until the earliest date of disease progression per RECIST v1.1 and irRECIST, or death due to any cause, if occurring sooner than progression.
- Overall survival determined from the Cycle 1 start date until death due to any cause.
- Response data in irradiated and non-irradiated lesions.
- Evaluation of various immune biomarkers from tumor and blood biospecimens.

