9.2 Statistical Methods and Properties

As of Amendment Version 09, this study will be conducted in 4 arms. Arms A, B, and C will each enroll an MTD expansion cohort. Arm D will have a dose de-escalation and MTD.

In Arm D, standard 3 +3 dose de-escalation and MTD will be applied for dose level 1 and -1 with standard MTD and DLTs rule. We will use CTCAE criteria to capture adverse events related to the study drugs. If cohort 1 is not tolerable, there will be de-escalation to cohort -1.

Each study treatment arm will have an MTD expansion cohort of up to 14 patients each. The expansion cohort for each arm will be stopped early if the aggregate DLT rate $> 33\%$ for that particular arm. The aggregate DLT rate for each arm will include patients that were treated at the same dose level in the dose escalation or de-escalation phase. If the trial does not stop early, we will estimate the disease control rate and the response rate separately for each cohort with appropriate 95% confidence intervals. We will also estimate the progression free survival (PFS) and overall survival (OS) distributions using the Kaplan-Meier product limit method and report summary measures such as the median value and probabilities at selected times (again with appropriate 95% confidence intervals).

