For the objective of describing the toxicity profile, descriptive statistics will be provided on the grade and type of toxicity by dose level. Clinical efficacy will be measured by objective tumor response per RECIST criteria. The clinical response is defined as a CR or PR or at least 6 months SD. A 95% confidence interval of response rate will be estimated based on a binomial distribution.

Table 12: Total Planned Accrual for Each Treatment Arm

Treatment Arm	Dose Escalation	MTD Expansion	Total Enrollment
Arm A: Avelumab + Utomilumab (4-1BB)	NA (Escalation at Pfizer)	N=8 (Prior to Amendment Version 06)	24
		N=16 (As of Amendment Version 06)	
Arm B: Avelumab + PF-04518600 (OX40)	NA (Escalation at Pfizer)	N=12 (Prior to Amendment Version 06)	28
		N=14 (As of Amendment Version 06) *Treated 16 after replacing 2 patients with IND Office Approval	
Arm C: Avelumab + Utomilumab (4-1BB) + PF-04518600 (OX40)	N=4 NA (Escalation at Pfizer)	N=11 (Prior to Amendment Version 06)	32
		N=14 (As of Amendment Version 06) *Treated 17 after replacing 3 patients with IND Office Approval	
Arm D: Avelumab + Utomilumab (4-1BB) + XRT		N=4 (Prior to Amendment Version 08)	33
		N=3 (On Amendment 08)	

Treatment Arm	Dose Escalation	MTD Expansion	Total Enrollment
	N=12 (As of Amendment 09)		
Arm E: Avelumab + PF-04518600 (OX40) + XRT	N=3 (Prior to Amendment Version 08)	Closed per Amendment Version 09	6
	N=3 (On Amendment 08)		
Arm F: Avelumab + Utomilumab (4-1BB) + PF-04518600 (OX40) + XRT	N=4 (Prior to Amendment Version 08)	Closed per Amendment Version 09	7
	N=3 (On Amendment 08)		
Total	36	92	128

MDACC Investigational New Drug (IND) Office, Medical Affairs and Safety Group will review safety and efficacy data with Principal Investigator (and statistician if needed), at a predetermined interval as indicated next:

PHASE I

The first analysis will occur after the first 3 evaluable subjects per arm (Arm D), are treated for 56 days from Cycle 1 Day 1 and prior to advancing/changing dose levels; and every 3 evaluable subjects thereafter.

PHASE II

Efficacy/toxicity analysis will occur every 7 evaluable subjects per arm when treated for 6 months after the first study therapy dose. Assess toxicity at the end of the first 56 days following Cycle 1 Day 1, and response after 6 months of treatment. On every report submission, the information from previous reported patients will need to be updated for response.

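### Section 9 gives two definitions of clinical response and two primary efficacy populations, and its time-0 censoring rule, read literally, overrides death as a PFS event

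*Combined protocol and SAP*

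**What the plan says.** **Response.** Section 9.3: "The clinical response is defined as a CR or PR or at least 6 months SD". Section 9.5.1: "The clinical response is defined as a CR or PR or SD". In both places the next sentence is the same: "A 95% confidence interval of response rate will be estimated based on a binomial distribution". The secondary endpoint in section 2.2.2 is "Objective response rate determined by radiographic disease assessments per RECIST v1.1 and irRECIST". Section 9.2 says "we will estimate the disease control rate and the response rate separately for each cohort", but the protocol does not define disease control. The primary objective in section 2.1.1 uses clinical benefit, whose last components are "partial response [PR], or stable disease [SD] for > 6 months"; section 9.7 uses the same threshold.

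**Population.** Section 9.1 bases the main efficacy inference on the per-protocol population. Section 9.5 bases the main efficacy analysis on a treated population: at least one dose of every assigned drug, plus some efficacy data after baseline. The treated population is not among the sets listed in 9.1, which mentions it only as a comparison. Section 9.1 also has a Response Analysis Set, in which patients taken off study for progression before any on-study scan count as failures.

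**Censoring.** Section 9.4 plans no imputation of missing efficacy data. It then censors at time 0, in time-to-event analyses generally, any patient without an efficacy evaluation. Section 2.2.2 makes death from any cause an event for PFS and for OS. The first scheduled scan is at 8 weeks (section 7.2).

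**The concern.** Two analysts following the plan could report different response rates, denominators and PFS curves from the same cohort of up to 14 patients, each with a sentence in section 9 to cite. If the choice is made once the data are visible, the most favourable version is available. Under 9.5.1 every patient with stable disease at a scan, however brief, counts towards clinical response. Both the treated population and the censoring rule can remove patients who fail early, which pushes the estimates upward.

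The stakes are limited. Response, PFS and OS are secondary and descriptive. Section 3.5 does base the recommended phase 2 dose partly on preliminary efficacy, but without a threshold, and Tables 3 to 5 label the Arm A to C doses as already determined. That argument therefore mainly concerns Arm D.

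**Working it through.** The plan states no sample size, power or error rate that rests on these rules, so there is no figure to reproduce. The passages were compared and the effects sized as follows.

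**1. Response definition, on the protocol's own counts.** Section 1.2.3 (PF-04518600 monotherapy): "Out of 25 patients evaluable for response, 1 patient experienced partial response", and 15 had stable disease. No CR is reported. Intervals are exact (Clopper-Pearson) 95%.

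| Definition | Count | Rate (95% CI) |
|---|---|---|
| CR+PR (ORR) | 1/25 | 4% (0.1–20%) |
| Section 9.3 (SD of at least 6 months) | at most about 6/25 | 24% (9–45%) |
| Section 9.5.1 (any SD) | 16/25 | 64% (43–82%) |

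The middle row is a ceiling. The same paragraph reports only 5 patients treated for more than 13 weeks. If SD is counted on treatment, no more than those 5 plus the 1 PR could meet 9.3 at that cut, and 13 weeks is well short of 6 months.

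**2. Response definition, cohort of 14.** Assume 2 CR/PR, 2 SD of at least 6 months and 5 shorter SD.
- CR+PR: 2/14 = 14.3% (1.8–42.8%)
- Section 9.3: 4/14 = 28.6% (8.4–58.1%)
- Section 9.5.1: 9/14 = 64.3% (35.1–87.2%)

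**3. Population.** Both populations are called primary, and their entry conditions differ. Per-protocol requires compliance with assessments and no major violation, and the first paragraph under that set also requires a DLT or completion of 56 days. Treated requires efficacy data after baseline. Neither adopts the failure-counting rule of the Response Analysis Set. The treated set's condition can drop a patient who fails before the first evaluation.

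**4. Censoring.** A patient censored at time 0 is in no risk set, so the rule is equivalent to exclusion. Suppose *k* of *n* patients die before any evaluation and no one else is censored earlier. After those deaths, correct S(t) = (1 − k/n) × reported S(t). The inflation factor is 1/(1 − f) with f = k/n:
- 1 of 14: 1/(1 − 1/14) = 14/13 = 1.08
- 2 of 14: 1/(1 − 2/14) = 14/12 = 1.17

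Check at week 8 with n = 14, assuming 4 progressions at the first scan:

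| Deaths before any evaluation | Deaths as events | Censored at time 0 |
|---|---|---|
| 1 | 9/14 = 64.3% | 9/13 = 69.2% |
| 2 | 8/14 = 57.1% | 8/12 = 66.7% |
| 3 | 7/14 = 50.0% | 7/11 = 63.6% |

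**5. How many such deaths?** The documents do not say. As an illustration, assume exponential survival with the median OS values in section 1.2.1 (avelumab, NSCLC): 8.4 months overall (36.5 weeks) and 4.6 months in PD-L1-negative patients (20.0 weeks). A dose of each drug is required and avelumab starts on Day 15, so condition on being alive at week 2. The probability of dying in weeks 2 to 8 is 1 − 2^(−6/median in weeks).
- 8.4 months: 1 − 2^(−6/36.5) = 10.8%; factor 1/(1 − 0.108) = 1.12
- 4.6 months: 1 − 2^(−6/20.0) = 18.8%; factor 1/(1 − 0.188) = 1.23

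These factors assume that none of those patients was evaluated. They are smaller if some had an unscheduled or end-of-treatment scan.

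**The case against.** The two response definitions and the two primary populations cannot be argued away from the text. The best defence concerns the rest.

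*Response rate could simply mean CR+PR.* That is the natural reading, and 9.2 lists disease control separately. But the sentence immediately before each planned interval defines clinical response with SD included, so the text does not establish that reading.

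*Section 9.1 already compares the two populations and counts progression before a scan as failure.* Both points are true, and they mean that both results should be available. They do not settle which is primary, and the failure rule belongs to a third set.

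*The censoring sentence is a missing-data rule, and a recorded death is not missing.* This has force. The sentence follows the statement on imputation, and an analyst could let the specific definition in 2.2.2 govern. Death might also count as efficacy data after baseline for the treated population, since OS is among the efficacy assessments in 2.1.2. No passage says so. This part is a conditional ambiguity, not a certain bias.

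A reader might infer three stronger things that the documents do not support:
- That the 9.3 rate could lie anywhere up to 64%. The count treated beyond 13 weeks caps it near 24% at that cut if SD is counted on treatment.
- That 10.8% is an upper bound on early deaths. The protocol's own 4.6-month median gives 18.8%.
- That progression without a scan should also become a PFS event. Section 2.2.2 rests progression on radiographic assessment, so that would change the endpoint rather than reconcile the text.

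**Conclusion.** Wrong as written and worth fixing. The conflicts over response and population stand on the text alone. The response definition matters most: 4%, at most about 24%, or 64% on the same 25 patients. These counts come from an interim cut of a monotherapy dose-escalation study with 11 patients still on treatment. They show how far apart the definitions lie and do not forecast this trial's ORR.

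The censoring conflict is conditional. If patients die without an efficacy evaluation, remain in the analysis population and 9.4 is applied literally, later PFS is inflated by 1.08 for 1 of 14 or 1.17 for 2 of 14. If the treated population has already dropped them, the same bias enters through 9.5. The illustrated range of 1.12 to 1.23 rests on borrowed NSCLC medians, exponential survival and no scans before death. Read literally, 9.4 also reaches OS, which needs no scan.

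It would go too far to infer that trial decisions are compromised: no decision rule or stated power uses these endpoints, and the Arm D DLT and MTD objective is unaffected.

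**What to change.** - **Sections 9.3 and 9.5.1:** define response rate as CR+PR, reported under RECIST 1.1 and under irRECIST. Report clinical benefit (CR, PR or SD for more than 6 months, as in 2.1.1 and 9.7) separately. Define the disease control rate named in 9.2.
- **Sections 9.1 and 9.5:** name one primary efficacy population, without the condition of efficacy data after baseline. Count its patients without a post-baseline assessment as non-responders, and report the other sets as sensitivity analyses.
- **Section 9.4:** state that death is a PFS event on the date of death whether or not an evaluation exists; that only patients alive with no post-baseline evaluation are censored at Day 1; and that the rule does not apply to OS, which is censored at the date last known alive.

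The cost is wording only, with no new data. Reported response rates may be materially lower than under 9.5.1, and PFS slightly lower.

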9.6 Safety Analysis

The safety population will consist of all patients who have received any amount of study medication.

9.6.1 Safety Evaluation

Safety analyses will be conducted using the Safety Population. For the objective of describing the toxicity profile, descriptive statistics will be provided on the grade and type of toxicity by dose level.

9.6.2 Adverse Events

Adverse Events (AEs) will be coded using the NCI-CTCAE (4.03) dictionary and displayed for all study patients combined. Analyses of AEs will be performed for those events that are considered treatment emergent, where treatment-emergent is defined as any AE with onset or worsening of a pre-existing condition on or after the first administration of study medication through 30 days following last dose or any event considered drug-related by the investigator through the end of the study. AEs with partial dates will be assessed using the available date information to determine if treatment-emergent; AEs with completely missing dates will be assumed to be treatment-emergent.

AEs will be summarized by patient incidence rates, therefore, in any tabulation, a patient contributes only once to the count for a given AE preferred term. The number and percentage of patients with any treatment-emergent AE will be summarized for all study patients combined. The number and percentage of patients with treatment-emergent AEs assessed by the Investigator as at least possibly related to treatment will also be tabulated. The number and percentage of patients with any grade ≥ 3 treatment-emergent AE will be tabulated in the same manner. In the event a patient

experiences repeated episodes of the same AE, then the event with the highest severity and/or strongest causal relationship to study treatment will be used for purposes of tabulations.

Serious AEs will also be tabulated.

No formal hypothesis-testing analysis of AE incidence rates will be performed. All AEs (treatment emergent and post-treatment) will be listed in patient data listings. By-patient listings will be provided for the following: patient deaths; serious AEs; and AEs leading to withdrawal.

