9.6.3 Laboratory Data

The actual value and change from baseline to each on study evaluation will be summarized for each clinical laboratory parameter, including hematology and clinical chemistry, for all study patients combined. In the event of repeat values, the last non-missing value per study day/time will be used.

Severity of select clinical lab measures will be determined using CTCAE criteria (e.g. those measures that have a corresponding CTCAE grade classification). Labs with CTCAE grades greater than or equal to 3 will be presented in a data listing. Shift tables that present changes from baseline to worst on-study values relative to CTCAE classification ranges will be produced.

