9.6.4 Vital Signs and Physical Examinations

The actual value and change from baseline to each on study evaluation will be summarized for vital signs for all study patients combined. By-patient listings of vital sign measurements will be presented in data listings.

Physical examination results at screening will be summarized; all other abnormal physical examination data were to be recorded on the AE eCRF. All examination findings will be presented in a data listing.

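### Sections 9.6.2 to 9.6.4 specify adverse event, laboratory and vital-sign summaries only for all patients pooled, which does not fit the Arm D safety objective, the by-dose-level toxicity summary or the per-arm final analysis

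*Combined protocol and SAP*

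**What the plan says.** Section 2.1.1 opens the primary objectives with "For Arm D, to establish the safety, tolerability, and dose-limiting toxicities (DLTs) of different treatment combinations of avelumab", in order to estimate the MTD and select the RP2D. Section 2.2.1 makes the corresponding endpoint the frequency, duration and severity of adverse events (AEs).

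The AE section, 9.6.2, states "Adverse Events (AEs) will be coded using the NCI-CTCAE (4.03) dictionary and displayed for all study patients combined" and then "The number and percentage of patients with any treatment-emergent AE will be summarized for all study patients combined". Grade 3 or higher events follow the same pattern. The tabulations of treatment-related and serious events state no grouping. Laboratory summaries in 9.6.3 are described as "including hematology and clinical chemistry, for all study patients combined". Section 9.6.4 says that actual values and changes from baseline "will be summarized for vital signs for all study patients combined".

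Other sections work on a finer unit:

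- Section 9.6.1, and 9.3 in the same words: "descriptive statistics will be provided on the grade and type of toxicity by dose level".
- Table 7 (Section 3.5) counts DLTs per dose level and separately for each arm.
- Sections 3.3 and 9.2 compute an aggregate DLT rate per arm.
- Section 9.3 sets toxicity reviews after every 3 evaluable patients in Arm D (Phase I) and every 7 per arm (Phase II).
- Section 9.8 plans the final analysis arm by arm.

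**The concern.** A treatment-emergent AE (TEAE) percentage pooled over this trial describes no regimen. The pool contains utomilumab at 100 mg (Arms A and D) and at 20 mg (Arm C), regimens with and without PF-04518600, irradiated and non-irradiated patients, two closed arms, and cohorts on abandoned avelumab or radiation schedules. The plan itself treats those schedules as distinct: new cohorts of Arms A to C were enrolled and the Arm D de-escalation was restarted when dosing changed (Sections 3.2.1 to 3.2.4).

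At stake is whether the primary safety endpoint is reported for the arm the objective names. If the tables are produced as written, an excess of AEs in Arm D would be averaged with a much larger group on other treatments. The final analysis of an arm under 9.8 would have no TEAE, laboratory or vital-sign table of its own.

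**Working it through.** **1. The plan's own denominator.** Inputs are from Table 12 and Section 9.3. The Arm D expansion size of 14 is from Section 3.2.4, because that cell is not legible in the text available; it agrees with the Arm D row total of 33 = 4 + 3 + 12 + 14.

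- Escalation: 4 (Arm C) + 4 + 3 + 12 (Arm D) + 3 + 3 (Arm E) + 4 + 3 (Arm F) = 36.
- Expansion: (8 + 14) Arm A + (12 + 16) Arm B + (11 + 17) Arm C + 14 Arm D = 92.
- Total: 36 + 92 = 128, as stated.

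This uses 14 new-schedule patients in Arm A (Section 3.2.1). Table 12 prints 16, and its row totals sum to 24 + 28 + 32 + 33 + 6 + 7 = 130. That is a separate discrepancy; I use the stated 128.

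**2. Share of Arm D in the pool.**

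- All Arm D schedules: 33/128 = 25.8%.
- Current schedule (Version 09): 12 + 14 = 26; 26/128 = 20.3%.
- Most at one radiation level: 6 + 14 = 20; 20/128 = 15.6%.

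**3. Share from closed arms or superseded schedules.** Arms A to C expansion before Version 06: 31. Arm C escalation before Version 05: 4. Arm D before Version 09: 4 + 3 = 7. Arms E and F: 6 + 7 = 13. Total 31 + 4 + 7 + 13 = 55; 55/128 = 43%.

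**4. Dilution.** Pooled rate = (26 × Arm D rate + 102 × rate elsewhere) / 128. The rates are assumptions.

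| Arm D rate | 10% elsewhere | 15% elsewhere | 20% elsewhere |
|---|---|---|---|
| 30% | 18.0/128 = 14.1% | 23.1/128 = 18.0% | 28.2/128 = 22.0% |
| 40% | 20.6/128 = 16.1% | 25.7/128 = 20.1% | 30.8/128 = 24.1% |

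In every cell the pooled figure lies closer to the rate outside Arm D than to the rate in Arm D.

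**5. Does the by-dose-level summary supply the missing split?** Only in part. Table 6 gives Arm D its own levels, 1 and -1. But Tables 3, 4 and 5 give Arms A, B and C one identical dose-level label, saying that the dose was determined by Pfizer, so the label does not separate three different regimens. No section says where patients on superseded Arm D schedules, or in Arms E and F, would be placed. The summary covers grade and type of toxicity, while TEAE incidence, laboratory values and vital signs remain expressly pooled.

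**6. Do the per-arm DLT rates supply it?** No. DLTs are selected events in the 56 days from Cycle 1 Day 1. TEAEs run to 30 days after the last dose, and to the end of study if drug-related (Section 9.6.2).

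**The case against.** A reader might infer that the primary safety endpoint is never estimated for Arm D or for any single regimen, and that no section separates safety by arm. The documents do not support that. The section immediately before the pooled tables promises grade and type of toxicity by dose level. Those quantities overlap substantially with the frequency and severity named in the endpoint, and Arm D has its own two levels. DLT rates, the stopping rule and the toxicity reviews are all per arm. One can also argue that each arm's dosing table carries its own dose-level column, so dose level is implicitly within arm.

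Nor do the documents say that the MTD or RP2D will be chosen from the pooled TEAE table. The MTD uses DLTs per level, and Section 3.5 bases the RP2D on safety and preliminary efficacy data from the escalation and expansion cohorts. By-patient listings of all AEs are planned, the tables are descriptive with no testing, and the dilution figures rest on assumed rates.

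All of this limits the consequence, and the claim that Arm D safety is wholly unestimated falls. The inconsistency remains. The implicit reading of dose level is reasonable for Arm D's current schedule, but it is not stated and does not deal with superseded schedules. The reviews are monitoring rather than the endpoint analysis, and listings are not a summary. An arm-by-arm final analysis makes all-patients tables harder to reconcile, not easier.

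**Conclusion.** The point holds as an inconsistency in a stated rule. Sections 9.6.2 to 9.6.4 prescribe pooled AE, TEAE, laboratory and vital-sign summaries. These do not fit the Arm D objective in 2.1.1, the by-dose-level summary in 9.3 and 9.6.1, or the per-arm final analysis in 9.8. Current-schedule Arm D contributes at most about one fifth of the pool, and 43% of planned accrual comes from closed arms or superseded schedules. Both shares assume that planned maximum accrual is reached. Under the assumed rates, an Arm D rate of 40% would appear as 16.1% to 24.1%, and one of 30% as 14.1% to 22.0%.

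This should be corrected before analysis. It is not a fatal fault, because per-arm DLT rates and a by-dose-level toxicity summary are already planned and the data needed for the split are already collected.

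**What to change.** - In 9.6.2 to 9.6.4, replace the all-patients grouping with summaries by treatment arm and, within arm, by dosing-schedule version (and by radiation level in Arm D). Keep a total column only as a supplement.
- Apply the same grouping to the related, grade 3 or higher and serious event tables.
- In 9.3 and 9.6.1, state that dose level means dose level within arm and schedule version.
- Name the Arm D current-schedule AE table as the primary safety analysis.

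The cost is SAP wording and more table columns; no new data are needed. The price is small denominators: with 8 events in 20 patients (40%), the exact 95% interval is 19.1% to 63.9%. That width is the real precision available for one Arm D radiation level, and pooling with other regimens does not improve it.
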